#### Table GBGF 5.3. Vitals Threshold for Study H9X-JE-GBGF

Systolic Blood Pressure (mm Hg)	-
≥140	
Diastolic Blood Pressure (mm Hg)	
≥90	
Pulse Rate (beats per minute)	
>100	

#### 5.14.6. Adjudication of safety events

Deaths, cardiac biomarkers, possible cases of pancreatitis, and non-fatal cardiovascular AEs will be adjudicated by an outside judgment committee external to Lilly. A listing of events that were sent for adjudication will be presented including the event as it was reported and how it was adjudicated.

#### 5.14.7. Renal safety

The following biomarker will be assessed:

- Serum creatinine
- Estimated glomerular filtration rate (eGFR) estimated by Modification of Diet in Renal Disease (MDRD) formula using the coefficient for Japanese (Matsuo et al., 2009)
- Urinary albumin to creatinine ratio (UACR)

eGFR (mL/min/1.73 m^2) = 175\*[serum creatinine-1.154]\*[age-0.203]\*[0.742 if female]\*[ 0.808 if Japanese]

Mean and mean change from baseline to endpoint of serum creatinine, eGFR, and UACR by treatment will be presented. Proportions of patients shifting between CKD stages by eGFR from baseline by treatment will be presented.

Shift tables based on eGFR and UACR (Table GBGF 5.4 and Table GBGF 5.5) will be provided (CKD risk stratification in JSN 2012).

GFR Stage	eGFR (mL/min/1.73 m  )
G1	≥90
G2	$60 \ge$ and $< 90$
G3a	$45 \ge$ and $< 60$
G3b	$30 \ge$ and $< 45$
G4	$15 \ge$ and $< 30$
G5	<15

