## 6.2. Exclusion Criteria

Patients will be excluded from study enrollment if they meet any of the following criteria at Visit 1:

- [10] have type 1 diabetes (based on WHO diagnostic criteria);
- [11] have previously received therapy with a GLP-1 receptor agonist within 3 months prior to Visit 1;
- [12] have been previously treated with dulaglutide prior to Visit 1;
- [13] have been treated with 2 of the following at Visit 1: DPP-4 inhibitor, SU, and glinide (ie, DPP-4 inhibitor and SU, or DPP-4 inhibitor and glinide);
- [14] have been treated with continuous subcutaneous insulin infusion at Visit 1;
- [15] have been treated with drugs that promote weight loss within the 3 months prior to Visit 1;
- [16] are receiving chronic ( $>14$  days) systemic glucocorticoid therapy (excluding topical, intraocular, or intranasal preparations) or have received such therapy within the 4 weeks prior to Visit 1;
- [17] have 1 or more episodes of severe hypoglycemia within the 6 months prior to Visit 1;
- [18] have 1 or more episodes of diabetic ketoacidosis within the 6 months prior to Visit 1;
- [19] have had any of the following cardiovascular conditions within the 3 months prior to Visit 1: acute myocardial infarction (MI), New York Heart Association (NYHA) Class III or Class IV heart failure, or cerebrovascular accident (stroke);

- [20] have a known clinically significant gastric emptying abnormality or have undergone gastric bypass surgery or restrictive bariatric surgery;
- [21] have acute or chronic hepatitis, signs and symptoms of any other liver disease, or alanine aminotransferase (ALT) level >2.5 times the upper limit of the reference range, as determined by the central laboratory at Visit 1;
- [22] have a history of chronic pancreatitis or acute idiopathic pancreatitis, or were diagnosed with any type of acute pancreatitis within the 3 months prior to Visit 1;
- [23] have an estimated glomerular filtration rate (eGFR) <30 mL/min/1.73 m^2, calculated by the Japanese Society of Nephrology equation, as determined by the central laboratory; for participants on metformin, have moderate renal disease or renal dysfunction (for example, eGFR <60 mL/min/1.73 m^2) at Visit 1;
- [24] have any self or family history of type 2A or type 2B multiple endocrine neoplasia (MEN 2A or 2B) in the absence of known C-cell hyperplasia;

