#### 8.1.1. *Permanent Discontinuation from Study Treatment and Study*

Patients will be permanently discontinued from investigational product and from the study in the following circumstances:

- For inadvertently enrolled patients for whom it was determined that continued treatment with investigational product would not be medically appropriate (see Section 8.1.3);
- The patient misses more than 2 consecutive weekly injections of investigational product or more than 14 consecutive daily injections of insulin;
- The patient's fasting SMPG concentrations are consistently above the fasting plasma glucose threshold for at least 2 weeks (see Section 7.4.1.3)
- The patient becomes pregnant during the study, in which case, the patient must discontinue the study immediately and Lilly or its designee is to be informed immediately;
- The patient is diagnosed with acute pancreatitis or acute hepatitis;
- The patient develops Exclusion Criterion [23] (eGFR <30 mg/min/1.73m^2);
- The patient is diagnosed with C-cell hyperplasia or medullary thyroid carcinoma;
- The patient uses or needs to use additional antidiabetic medication or prohibited medication (for example, weight loss medication; see Section 7.7);
- The patient requires >14 days of therapy with systemic glucocorticoids;
- Enrollment in any other clinical trial involving an investigational product or enrollment in any other type of medical research judged not to be scientifically or medically compatible with this study;
- Sponsor decision
  - Sponsor stops the study or stops the patient's participation in the study for medical, safety, regulatory, or other reasons consistent with applicable laws, regulations, and good clinical practice (GCP)
- Investigator decision
  - The investigator decides that the patient should be discontinued from the study

- If the patient, for any reason, requires treatment with another therapeutic agent that has been demonstrated to be effective for treatment of the study indication, discontinuation from the study occurs prior to introduction of the new agent
- Patient decision
  - The patient requests to be withdrawn from the study

Discontinuation of the investigational product for abnormal liver tests **should be considered** by the investigator when a patient meets 1 of the following conditions after consultation with the Lilly CRP or CRS:

- ALT or aspartate aminotransferase (AST) >8X upper limit of normal (ULN)
- ALT or AST >5X ULN for more than 2 weeks

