#### Stored Samples

Pharmacogenomics sample

---

Abbreviations: CK-MB = creatine kinase-MB; eGFR = estimated glomerular filtration rate; HbA1c = hemoglobin A1c; RBC = red blood cells; SGOT = serum glutamic oxaloacetic transaminase; SGPT = serum glutamic pyruvic transaminase; WBC = white blood cells.

a All tests will be performed by the Lilly-designated central laboratory.

b Microscopic evaluation to be performed if any of the listed analytes are positive.

c Urinary albumin and creatinine are measured; ratio is calculated.

d Direct LDL-C is measured.

e Japanese eGFR equation defined by the Japanese Society of Nephrology is used to estimate glomerular filtration rate.

f CK-MB is to be assayed if creatine kinase result >1000 IU/L.

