#### Table GBGF 5.4. CKD Stage based on eGFR for Study H9X-JE-GBGF

#### Table GBGF 5.5. CKD Stage based on UACR for Study H9X-JE-GBGF

Albuminuria Stage	UACR (mg/g)
A1	<30
A2	$30 \ge$ and $< 300$
A3	≥300

The following threshold analyses (with eGFR by MDRD formula and UACR) will be presented:

- Postbaseline eGFR <60 mL/min/1.73 m^2
- Postbaseline eGFR <60 mL/min/1.73 m^2, or UACR >300 mg/g

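### SAP 5.14.7 computes eGFR by an MDRD formula, while the protocol uses the Japanese Society of Nephrology equation for entry, discontinuation and laboratory eGFR, and nothing reconciles the two

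*SAP*

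**What the plan says.** **SAP.** Section 5.14.7 lists eGFR "estimated by Modification of Diet in Renal Disease (MDRD) formula using the coefficient for Japanese" and prints the formula: 175 × creatinine^-1.154 × age^-0.203, times 0.742 for women, times a final factor given as "0.808 if Japanese". From this value it plans means and mean changes, shifts between CKD stages (with the stages referenced as "CKD risk stratification in JSN 2012"), and counts of patients below 60 after baseline. The choice is restated for the last of these: "The following threshold analyses (with eGFR by MDRD formula and UACR) will be presented".

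**Protocol.** Exclusion criterion 23 in section 6.2 sets its limit on an eGFR "calculated by the Japanese Society of Nephrology equation, as determined by the central laboratory". In Appendix 2, footnote e is attached to creatinine and reads "Japanese eGFR equation defined by the Japanese Society of Nephrology is used to estimate glomerular filtration rate". Footnote a adds "All tests will be performed by the Lilly-designated central laboratory". Section 8.1.1 carries the same criterion into permanent discontinuation, in the item that begins "The patient develops Exclusion Criterion [23".

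**The concern.** The trial names two eGFR equations for the same creatinine sample. One governs who enters, who must stop and what the laboratory derives. The other governs what the renal safety section reports. The protocol never mentions MDRD. The SAP does not say why it departs from the protocol's equation, or whether the laboratory eGFR will also be tabulated. It also takes its CKD stages from the JSN guide but assigns patients to them with an eGFR that it labels MDRD.

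The cut-offs coincide, so this is more than a matter of labels. Section 6.2 excludes everyone below 30 and gives below 60 as its example for metformin users. The SAP stages break at 30 and 60, and its threshold counts use 60. If the two values differ, two things could happen:

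- A metformin user admitted correctly with a laboratory eGFR just above 60 could appear as G3a at baseline. That patient could then count as below 60 after baseline with no change in renal function, because the threshold as written does not require a baseline value of 60 or more.
- A patient near 30 could appear as G4 without having met the discontinuation criterion, or could have met it while shown as G3b.

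A reader of the study report might take such cases for eligibility or discontinuation deviations, or for a renal signal.

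**Working it through.** There is no figure in the plan to reproduce, since neither document gives an expected eGFR or a count by stage. The check sets the texts side by side, evaluates the one printed formula, and runs a sensitivity range.

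**1. Which equation applies where**

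| Use | Equation named | Place |
|---|---|---|
| Entry (exclusion 23) | JSN, central laboratory | Protocol 6.2 |
| Permanent discontinuation | By reference to exclusion 23 | Protocol 8.1.1 |
| eGFR from laboratory creatinine | JSN | Protocol Appendix 2, footnote e |
| Means, mean changes, CKD shifts | MDRD × 0.808 | SAP 5.14.7 |
| Thresholds below 60 | MDRD, restated | SAP 5.14.7, after Table GBGF 5.5 |

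**2. The SAP formula as printed.** The SAP gives no unit for creatinine; mg/dL is assumed. The constant is 175 × 0.808 = 141.4, so eGFR = 141.4 × Cr^-1.154 × age^-0.203 (× 0.742 for women).

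- Man of 60, Cr 1.0: 61.6, stage G2
- Man of 60, Cr 1.2: 49.9, stage G3a
- Woman of 60, Cr 0.8: 59.1, stage G3a
- eGFR equals 30 at Cr 1.87 (man of 60) or 1.44 (woman of 60)

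Two of these examples fall within 2 units of the 60 cut.

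**3. Which values would be restaged.** The JSN coefficients are in neither document, so the actual gap cannot be computed. Assume laboratory eGFR = (1 + d) × SAP eGFR. A patient changes side of a cut t when the SAP value lies between t and t/(1 + d). For example, with d = -5% and t = 60, the limit is 60/0.95 = 63.2.

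| Assumed d | SAP values affected at 60 | SAP values affected at 30 |
|---|---|---|
| -10% | 60 to 66.7 | 30 to 33.3 |
| -5% | 60 to 63.2 | 30 to 31.6 |
| -2% | 60 to 61.2 | 30 to 30.6 |
| +2% | 58.8 to 60 | 29.4 to 30 |
| +5% | 57.1 to 60 | 28.6 to 30 |
| +10% | 54.5 to 60 | 27.3 to 30 |

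Applied to the examples, the man at 61.6 has a laboratory value of 61.6 × 0.95 = 58.5 if d = -5%, and moves from G2 to G3a. At d = -2% he stays in G2 (61.6 × 0.98 = 60.4). The woman at 59.1 moves from G3a to G2 at d = +2% (59.1 × 1.02 = 60.3).

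The table shows where a difference would matter. It does not show that a difference of any given size exists.

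**The case against.** The strongest reply is that the documents show two names, not two numbers. The JSN equation is not printed, the SAP formula carries a Japanese coefficient, and the paper it cites concerns GFR equations for Japan. This stands as a limit on size and direction. It does not reconcile the texts, because no statement in either document says the two agree.

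Second, no protocol analysis is contradicted. The protocol's safety analysis sections specify no eGFR or CKD-stage table, and section 10.3.1 allows additional exploratory analyses. A reader might infer a late or undisclosed switch, but the documents do not support that. The formula is printed in full, version 1 of the SAP was approved before the first patient visit, and the revision history lists no renal change in versions 2 or 3.

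Third, a reader might infer a biased treatment comparison. That is not supported either. One equation serves both arms at baseline and afterwards, and nothing suggests that it favours an arm. Serum creatinine, which needs no equation, is also summarised. SAP 5.14 limits safety p-values to guidance, and the HbA1c analysis does not use eGFR.

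Fourth, CKD stages are cut-points, and nothing in the documents ties them to one equation. A reasoned justification of MDRD would therefore remove the silence. It would still leave the renal tables on a different scale from the entry and discontinuation limits.

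**Conclusion.** The point holds as an unreconciled difference between protocol and SAP, and it is minor. If the two equations give different values, patients near 30 or 60 may be staged differently in the renal safety tables than by the eGFR used to admit or discontinue them.

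It is tempting to turn the restaging bands into a number of patients. The documents do not allow it. That would need the JSN coefficients and the eGFR distribution of the enrolled patients, and neither is given. A smooth assumed distribution would also ignore the trial's own exclusions, which act at the same cut-offs.

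The conclusion rests on the texts alone. The worked values assume creatinine in mg/dL, and the bands assume a proportional gap of 2% to 10% in either direction. Between-arm summaries stay internally consistent, and the effect is confined to descriptive safety output.

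**What to change.** In SAP 5.14.7, including the threshold analyses that follow Table GBGF 5.5, use the protocol's JSN eGFR for means, mean changes, shift tables and thresholds. Take the central-laboratory value where it is reported. Otherwise recompute it from central-laboratory creatinine at each scheduled chemistry visit (Visits 1, 3, 7, 10, 12 and 13, and early termination). Print the equation with its creatinine unit. Keep MDRD only as a labelled sensitivity table, with a sentence on why it is shown.

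The cost is SAP wording and some programming. Creatinine is already in the scheduled chemistry panel, so no new samples or visits are needed, and the protocol text can stay as it is. The downside is one extra set of tables if the MDRD version is kept.

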#### Table GBGF 5.4. CKD Stage based on eGFR for Study H9X-JE-GBGF

#### Table GBGF 5.5. CKD Stage based on UACR for Study H9X-JE-GBGF

Albuminuria Stage	UACR (mg/g)
A1	<30
A2	$30 \ge$ and $< 300$
A3	≥300

The following threshold analyses (with eGFR by MDRD formula and UACR) will be presented:

- Postbaseline eGFR <60 mL/min/1.73 m^2
- Postbaseline eGFR <60 mL/min/1.73 m^2, or UACR >300 mg/g

#### 5.15. Subgroup Analyses

Subgroup analyses will be conducted for the variables of HbA1c, body weight, and hypoglycemia rate.

The following are candidate subgroups that might be analyzed. This list is not necessarily all inclusive:

- Baseline HbA1c (<8.5%, ≥8.5%)
- Insulin regimen (basal insulin, premixed insulin, or basal/mealtime insulin).

For the subgroup analysis by insulin regimen, an analysis will be performed using an MMRM model or negative binomial regression model that includes the same effects given for primary or

secondary efficacy measures plus subgroup, subgroup-by-treatment interaction, subgroup-byvisit interaction, and subgroup-bytreatment-by-visit interaction. For the subgroup analysis by baseline HbA1c strata (<8.5%,  $\geq$ 8.5%), baseline HbA1c will not be included as a covariate. The treatment-by-subgroup interaction at Week 16 will be evaluated using a significance level of 0.10, unadjusted.

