## 5. A Priori Statistical Methods

## 5.1. Determination of Sample Size

A total of approximately 160 patients (dulaglutide: 120 patients; placebo: 40 patients) will be randomized to have approximately 136 completers (dulaglutide : 102 patients; placebo: 34 patients) to show dulaglutide is superior to placebo with more than 99% power assuming a treatment difference of 1.0% in HbA1c reduction, standard deviation (SD) = 1.0%, and dropout rate of 15%. The screen failure rate is estimated as 20%. Approximately 200 patients will be screened.

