#### 5.2. General Considerations

Statistical analysis of this study will be the responsibility of Lilly or its designee. Any change to the data analysis methods described in the protocol will require an amendment ONLY if it changes a principal feature of the protocol. Any other change to the data analysis methods described in the protocol, and the justification for making the change, will be described in the clinical study report (CSR). Additional exploratory analyses of the data will be conducted as deemed appropriate.

All analyses will be implemented using Version 9.1.3 SAS or higher.

Continuous data will be summarized in terms of the number of observations (n), mean, standard deviation (SD) and/or standard error of the mean (SEM), median, minimum (Min), and maximum (Max).

Categorical data will be summarized in terms of the number of observations (n), frequency count, and percentages. Percentages will be rounded to one decimal place. Percentages will not be presented for zero counts. Unless noted otherwise, percentages will be calculated using n (the number of observations with non-missing values) as denominator.

For efficacy analysis based on mixed-model for repeated measures (MMRM), summary statistics will be provided for the observed value and change from baseline value for each arm based on MMRM. Also, for efficacy analysis, statistical tests (including MMRM and ANCOVA) will only be conducted during the double-blind primary treatment period at each visit (i.e. Visit 4, 5, 6 and 7) and will not be conducted for time point after Visit 7.

For safety analysis, summary statistics will be provided for each arm during the both doubleblind primary treatment period (i.e. Visit 3 to 7) and entire study period (i.e. Visit 3 to 13). Table GBGF 5.1 gives the treatment groups to be displayed for each treatment period.

Unless otherwise specified, all tests of treatment effects will be conducted at a 2-sided alpha level of 0.05, and confidence intervals (CIs) will be calculated at 95%, 2-sided. All tests of interactions between treatment groups and other factors will be conducted at a 2-sided alpha level of 0.10. There will be no multiplicity adjustment for pairwise treatment comparisons.

List of analysis (LOA) will contain the list of all tables, figures and listings (TFLs), and will be provided separately.

			Between-Group Comparison When
Treatment Period	Treatment Groups	Abbreviation	Applicable
Double-blind	Placebo	Plc	Dula vs Plc

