#### 5.10.1.2. Primary Analysis Model

The primary analysis model will be an MMRM for HbA1c change from baseline to 16 weeks (Visit 7) using REML with treatment, insulin regimen (basal insulin, premixed insulin, or

basal/mealtime insulin), visit, and treatment-by-visit as fixed effects, baseline HbA1c as a covariate, and patient as a random effect.

An unstructured covariance structure will be used to model the within-patient variability and implicitly adjust for missing data. If this analysis fails to converge, the following covariance structures will be tested in order:

- Toeplitz with heterogeneity
- Autoregressive with heterogeneity, by visit
- Compound symmetry with heterogeneous variances, by visit
- Toeplitz
- Autoregressive
- Compound symmetry without heterogeneous variances, by visit.

The first covariance structure that converges will be used. The Kenward-Roger approximation will be used to estimate denominator degrees of freedom. Significance tests will be based on least squares (LS) means using Type III sum of squares.

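### For the HbA1c outcome, the subgroup model by baseline HbA1c stratum leaves out continuous baseline HbA1c and gives up a little precision that could be kept at almost no cost

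*SAP*

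**What the plan says.** The primary HbA1c model (Protocol 10.3.3.1, SAP 5.10.1.2) has treatment, insulin regimen, visit and treatment-by-visit, with "baseline HbA1c as a covariate, and patient as a random effect".

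SAP 5.15 plans subgroup analyses of HbA1c, body weight and hypoglycemia rate, with baseline HbA1c class and insulin regimen as candidate subgroups. The insulin-regimen subgroup model keeps the effects of the parent model and adds the subgroup with its interactions. For the HbA1c-class subgroup the only specific model instruction is that "baseline HbA1c will not be included as a covariate". Protocol 10.3.7 has the same rule, so the two documents agree. Neither gives a reason. On the test, the SAP says: "The treatment-by-subgroup interaction at Week 16 will be evaluated using a significance level of 0.10, unadjusted".

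The other two outcomes differ. The body-weight model (SAP 5.10.2) uses HbA1c only as the two-level class, plus baseline weight. The hypoglycemia-rate model (SAP 5.14.3) has no HbA1c term.

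**The concern.** Entry HbA1c at Visit 2 runs from 7.5% to 10.5% (Protocol 6.1), and a single cut at 8.5% leaves real variation inside each class. If patients with higher baseline HbA1c fall further, that variation goes into the residual unless the continuous value is also fitted. The stratum and the continuous value can stand in the same model.

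At stake is the precision of the stratum-specific HbA1c effects and of their interaction, in a trial with only 34 planned placebo completers across two strata. A lesser point is that the stratum effects come from a different adjustment than the primary result they are meant to explain.

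**Working it through.** **The plan's own figure.** SAP 5.1 claims "more than 99% power assuming a treatment difference of 1.0% in HbA1c reduction", with "standard deviation (SD) = 1.0%, and dropout rate of 15" percent. With 102 and 34 completers, SE = 1.0 × √(1/102 + 1/34) = 0.198. Power at two-sided 0.05 is Φ(1.0/0.198 − 1.96) = 0.999, so the claim reproduces. The documents state no power or precision for the interaction.

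**Method.** A Week 16 analysis of covariance stands in for the MMRM contrast:

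- With the covariate: SE(interaction) = s × √(sum of 1/n over the four treatment-by-stratum cells), where s is the residual SD.
- Without it: s becomes √(s² + b²w), where b is the slope of change on baseline and w is the pooled within-stratum variance of baseline.
- The ratio √(1 + b²w/s²) applies equally to a stratum-specific effect.

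**Inputs.** From the documents: 102 and 34 completers, SD 1.0, cut at 8.5%, range 7.5% to 10.5%, interaction alpha 0.10. Assumed: the slope, the baseline distribution (and so the stratum split), and the interaction size.

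**Two baseline distributions that bracket the range.**

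- Bell-shaped (normal, mean 8.3, SD 0.7, truncated to the range). Share above the cut 0.443; within-stratum SDs 0.277 and 0.379. w = 0.557 × 0.277² + 0.443 × 0.379² = 0.106. Cells 56.8, 45.2, 18.9 and 15.1; SE with covariate = √0.159 = 0.399.
- Flat over the range, an extreme. Share above the cut 0.667; within-stratum SDs 0.289 and 0.577. w = 0.333 × 0.289² + 0.667 × 0.577² = 0.250. Cells 34.0, 68.0, 11.3 and 22.7; SE with covariate = √0.176 = 0.420.

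In both, about a third of the baseline variance lies within strata.

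**Ratio of interaction SE, without over with the covariate, residual SD 1.0:**

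| Slope | Bell-shaped | Flat |
|---|---|---|
| 0 | 1.000 | 1.000 |
| -0.2 | 1.002 | 1.005 |
| -0.4 | 1.008 | 1.020 |
| -0.6 | 1.019 | 1.044 |
| -0.7 | 1.026 | 1.059 |

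For example, bell-shaped at -0.6: √(1 + 0.36 × 0.106) = 1.019, so the SE goes from 0.399 to 0.406.

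**Power at alpha 0.10, slope -0.6.** For an interaction of 0.5 points, omission lowers power from 35.0% to 34.1% (bell-shaped) or from 32.7% to 31.0% (flat). For 1.0 point, it goes from 80.6% to 79.3%, or from 76.9% to 73.7%.

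**Sensitivity to the SD.**

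- Residual SD 0.8, slope -0.6: 1.029 (bell-shaped) to 1.068 (flat).
- Residual SD 0.6, slopes -0.6 to -0.8: about 1.05 to 1.20.
- If 1.0 is read as the total SD of change, the residual variance is 1 − b² × (total baseline variance). At -0.7 this is 1 − 0.49 × 0.570² = 0.841 (bell-shaped) and 1 − 0.49 × 0.866² = 0.633 (flat). The ratios are √(1 + 0.052/0.841) = 1.03 and √(1 + 0.1225/0.633) = 1.09.

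**Simulation.** 6,000 runs per setting were made with stratified 3:1 allocation, residual SD 0.9, and Visit 3 baseline equal to the Visit 2 value plus noise of SD 0.2. Mean SE without versus with the covariate was 0.366 v 0.361 at slope -0.4 and 0.374 v 0.360 at -0.6. Power for an interaction of 0.5 was 38.6% v 40.2% and 38.2% v 40.3%. Type I error was 0.094 to 0.104, and the interaction estimate was unbiased, in both models. A second simulation over slopes 0 to -0.7 gave SE increases of about 0% to 5% at a total SD of 1.0 and up to about 9% at 0.8.

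**The case against.** The best defence is that this is a stated choice, the same in both documents, for candidate subgroup analyses tested without adjustment and without any power claim. HbA1c adjustment is coarsened rather than removed, since the stratum stays in the model. SAP 5.2 already allows additional exploratory analyses, so an adjusted version could be run anyway. All of this stands, and it is why the point is a small improvement and not an error.

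A reader might infer more, in four ways that the documents do not support:

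- **That the omission is what makes the interaction test weak.** It is not. Cell size is the main limit. With the covariate restored the SE is still about 0.4, and power for an interaction of 0.5 points is still only about a third at residual SD 1.0.
- **That all three subgroup outcomes are affected.** Body weight and hypoglycemia rate have no continuous HbA1c term in their parent models, so nothing is dropped there. For body weight, the sentence may simply avoid entering the same class twice.
- **That chance imbalance within strata is a separate harm.** Randomization is stratified on Visit 2 HbA1c (Protocol 7.2). Remaining imbalance within strata causes no bias, and its variability is already in the SE.
- **That the two terms are too collinear to fit together.** The simulation showed no harm to the interaction estimate with both in the model.

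**Conclusion.** The point holds for the HbA1c outcome only, as a minor loss of efficiency. At the planning SD of 1.0 and slopes of 0 to -0.7, omitting continuous baseline HbA1c raises the interaction SE by about 0% to 5%. A flat baseline distribution, which is an extreme, takes it to about 6% at a slope of -0.7, or 9% if 1.0 is the total SD. A smaller SD also raises it. If change does not depend on baseline, nothing is lost. The slope, baseline spread and stratum split are assumptions, since the documents give none of them.

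There is no bias, no type I error problem and no effect on the primary analysis. The case for change is that the baseline value is already collected and already in the primary model, and that no reason is given for leaving it out.

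**What to change.** Replace the sentence in SAP 5.15, and align Protocol 10.3.7, along these lines: *For the HbA1c outcome, the subgroup MMRM by HbA1c stratum includes the primary-model effects, including continuous baseline HbA1c, plus stratum and its interactions with treatment and visit.* Deleting the sentence is not enough: the list of retained effects is written for the insulin-regimen subgroup, so deletion would leave the HbA1c-stratum model with no specific covariate rule. If the sponsor prefers to omit the covariate, the reason should be given.

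The same edit could say whether the subgroup uses the Visit 2 value that stratified randomization or the Visit 3 baseline, because the label leaves this open.

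The cost is wording in two places. Under Protocol 10.3.1 and SAP 5.2, only a change to a principal feature needs an amendment, and other changes are justified in the study report. This one does not appear to be a principal feature. Timing matters more, since the SAP revision history shows that Version 3 already added post hoc analyses. If the data are already unblinded, keep the pre-stated model and report the adjusted one as a labelled sensitivity analysis.
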